9.3.10 Change from Baseline in SOFA Score

SOFA sub-score and total score actual values and change from baseline will be presented using descriptive statistics at Day 3, ICU discharge or Day 28 (whichever comes first).by treatment group. The change from baseline to Day 3 and to ICU Discharge or Day 28 difference between the two groups for each sub-score and for total score will be described.

A graph displaying the means and SD for each timepoint (until the subject is discharged from ICU) will be also provided for each treatment group.

9.3.11 Percentage of Subjects Alive and Organ Failure Free (SOFA score=0) at Day 28 or Discharge

The subject will be defined alive and organ failure free at Day 28 or Discharge if:

- Date of Death is missing or > MIN (Date of Day 28 or Date of Discharge)

AND

- Total SOFA Score = 0 at Day 28 or at Discharge

The percentage will be summarized.

9.3.12 Change from Baseline in Ventilatory Parameters

Ventilatory parameters actual values and change from baseline (TV, RR, Cdyn, Cstat, PEEP, PIP, and Pplat) will be presented using descriptive statistics by timepoint and treatment group.

A graph displaying the means and SD for each timepoint (until the subject is discharged from ICU) will be also provided for each treatment group and parameter.

9.3.13 Change from Baseline in Blood Gas Analysis Parameters

Acid-base balance blood gas analysis parameters actual values and change from baseline (pH, pCO₂, paO₂, HCO₃, lactate) will be presented using descriptive statistics by time point and treatment group.

9.4 Exploratory Efficacy Variables

Only for the UK subgroup of subjects:

Exploratory parameters from tracheal aspirates and blood samples:

- Surfactant Function measuring surface tension (mN/m) from TA samples.
- Mass spec lipid analysis (%) from TA samples.

- Protein D Enzyme Linked Immunosorbent Assay (ng/mL) from TA samples.
- Surfactant Protein D Enzyme Linked Immunosorbent Assay (ng/mL) from Blood samples.

will be summarized by actual and change from baseline values by treatment group at each time point using descriptive statistics on ITT set.

Cytospin values will only be listed.

In case of sample not done or if some values are under the lower limit of quantitation (BLOQ), the values will be considered as missing data.

10 Safety Analyses

Safety analysis will be based on the Safety Set.

10.1 Extent of Exposure

The number of poractant alfa drug administrations (1, 2 or 3) will be presented using frequencies for the poractant alfa group. Actual diluted volume administered (ml) will be summarized using summary statistics.

10.2 Adverse Events

An adverse event (AE) will be classified as follow:

- For poractant alfa group:
 - Pre-treatment AE: if it starts before the first study medication administration (AE onset date/time < date/time of first study medication administration);
 - Treatment emergent AE (TEAE): if it starts on or after the first dose of study medication administration (AE onset date/time \geq date/time of first study medication administration).
- For control group:
 - Pre-treatment AE: if it starts before the randomisation date (AE onset date/time < start date/time of randomisation);
 - Treatment emergent AE (TEAE): if it starts on or after the randomization date (AE onset date/time \geq start date/time of randomisation).

An adverse drug reaction (ADR) is an AE related to study medication. A serious ADR is a serious AE (SAE) related to study medication.

A severe AE is an AE with severe intensity. Refer to Section 7.3 for missing severity.

An AE leading to discontinuation is an AE with action taken with study drug equal to “Drug Permanently Withdrawn”.

An AE leading to death is an AE with outcome equal to “Fatal”.

Pre-treatment AEs, and TEAEs will be presented separately. Pre-treatment AEs will be presented in the listings only.

Two AEs with the same PT and classified in the same category (pre-treatment AE or TEAE) will be considered as two different events when calculating the “number of events” in the tables.

A summary table displaying the number and the percentage of subjects experiencing at least one TEAE, serious TEAEs, non-serious TEAEs, ADRs/drug-related TEAE, serious ADRs, severe TEAEs, TEAEs leading to study drug discontinuation and TEAEs leading to death, as well as the number of events, will be presented by treatment group.

The SOC and PT will also be used for tabulation using the MedDRA dictionary. The number and percentage of subjects with at least one AE and the number of events will be presented by SOC and PT by treatment group for treatment emergent AEs, non-serious TEAEs, serious TEAEs, ADRs, serious ADRs, severe TEAEs, TEAEs leading to treatment discontinuation and TEAEs leading to death.

A table presenting the number and percentage of subjects with at least one TEAE will be provided by PT. The number of subjects with TEAEs will be also displayed by SOC and PT and maximum severity. The number of events will be also included in these analyses.

Tables will be presented by SOC and then by PT, alphabetically sorted.

In addition, TEAEs that are presented by PT will be sorted by decreasing overall frequency.

An individual subject listing will also be provided for AEs.

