6.2.3 Administration

Before treatment, patients transiently will receive 100% oxygen.

Poractant alfa boluses, 30 mg per kilogram of lean body weight, will be administered through a sterile syringe connected to an opaque catheter inserted into the endotracheal tube with the distal end approximately 1cm above the carina. The first half of the dose will be administered during a pause in mechanical ventilation in which PEEP will be maintained and the patient will be in the left or right lateral decubitus position, and the second half will be administered similarly 5 minutes later, with the patient in the opposite lateral decubitus position [20].

When possible, tube suctioning should be avoided for 3 hours after the administration.

Patients will receive a total of three administrations, 24 hours apart.

For details on study medication dosage and administration please refer to the IMP Management manual.

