In case the patient will be assigned to the poractant alfa treated group, the treatment must start soon after the randomization (max 2 hr), and within 48hr after intubation

The following procedures for treated group or for control group will be conducted according to the frequencies reported in the above flowchart:

- Treatment procedure for poractant alfa as described in detail in [section 6.2](#). One administration per day with a 24 hours interval
- Arterial Blood Gas (ABG) Analysis
- Ventilatory support
- Ventilatory parameters: PaO₂/FiO₂, FiO₂, tidal volume (TV), respiratory rate (RR), static compliance (Cstat), dynamic compliance (Cdyn), PEEP (positive end-expiratory pressure), PIP (peak inspiratory pressure), Plateau Pressure (Pplat)
- Laboratory assessments for mechanistic analysis: blood sampling and bronchial washings; bronchoscopic washings performed as clinically indicated only, with surplus samples retrieved for mechanistic study as available (for more details ref. to [section 7.2](#))

Clinical Study Code No.: CLI-050000-04	Version No.: 4.0
EUDRACT No.: 2020-002632-75 – IND No: 153286	Date: 02 MAR 2021

- Laboratory assessments: blood count, bilirubin, creatinine, eGFR, LDH, D-dimer, CRP, procalcitonin
- Vital signs will be obtained as appropriate
- SOFA score is calculated considering PaO₂/FiO₂, Glasgow coma scale, mean arterial pressure, and bilirubin, platelet and creatinine levels
- AEs review (including SAEs)
- Concomitant medications and procedure review as applicable

7.1.3 Day 4 – 27 recording:

The following procedures for treated group or for control group will be conducted according to the above flowchart

- Arterial Blood Gas (ABG) Analysis
- Ventilatory support: extubation date recorded (as applicable) and following ventilation procedures recorded
- Ventilatory parameters: PaO₂/FiO₂, FiO₂, tidal volume (TV), respiratory rate (RR), static compliance (Cstat), dynamic compliance (Cdyn), PEEP (positive end-expiratory pressure), PIP (peak inspiratory pressure), Plateau Pressure (Pplat)
- Vital signs will be obtained as appropriate
- AEs review (including SAEs)
- Concomitant medications and procedure review as applicable
- Discharge date from ICU if applicable

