Listing 16.2.7.1	Pre-treatment Adverse Events (Intention-To-Treat Set)	AEL001	
 - Remove 'Ethnicity', 'Pattern'. - Replace 'Concomitant Therapy' 'Concomitant Procedure' by 'Concomitant Therapy / Concomitant Procedure' - Concatenate AEACN with AEACNOTH (Action taken : <specify>) 	Add the footnotes: [1] CA = Is a congenital anomaly or birth defect; DI = Results in persistent or significant disability or incapacity; DTH = Results in death; HSP = Requires hospitalization or prolongation of existing hospitalization; LTH = Is life-threatening; SIG = Is a medically significant adverse event. [2] System Organ Class and Preferred Term are coded using MedDRA Version 23.0.
Listing 16.2.7.2	Treatment Emergent Adverse Events (Intention-To-Treat Set)	AEL002	
 - Remove 'Ethnicity', 'Period/Actual Treatment', 'Starting dose/dose at onset/weight' and 'Pattern'. - Replace 'Concomitant Therapy' 'Concomitant Procedure' by 'Concomitant Therapy / Concomitant Procedure' - Concatenate AEACN with AEACNOTH (Action taken : <specify>) 	Same as Listing 16.2.7.1
Listing 16.2.7.3	Serious Treatment Emergent Adverse Events (Intention-To-Treat Set)	AEL002	Same as Listing 16.2.7.2	Same as Listing 16.2.7.1
Listing 16.2.7.4	Non-Serious Treatment Emergent Adverse Events (Intention-To-Treat Set)	AEL002	Same as Listing 16.2.7.2	Same as Listing 16.2.7.1

Listing Number	Listing Title	Template Code	Notes	Footnotes
Listing 16.2.7.5	Treatment Emergent Adverse Drug Reactions (Intention-To-Treat Set)	AEL002	Same as Listing 16.2.7.2	Same as Listing 16.2.7.1
Listing 16.2.7.6	Serious Treatment Emergent Adverse Drug Reactions (Intention-To-Treat Set)	AEL002	Same as Listing 16.2.7.2	Same as Listing 16.2.7.1
Listing 16.2.7.7	Severe Treatment Emergent Adverse Events (Intention-To-Treat Set)	AEL002	Same as Listing 16.2.7.2	Same as Listing 16.2.7.1
Listing 16.2.7.8	Treatment Emergent Adverse Events Leading to Study Drug Discontinuation (Intention-To-Treat Set)	AEL002	Same as Listing 16.2.7.2	Same as Listing 16.2.7.1
Listing 16.2.7.9	Treatment Emergent Adverse Events Leading to Death (Intention-To-Treat Set)	AEL002	Same as Listing 16.2.7.2	Same as Listing 16.2.7.1

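### SAP 10.2 counts adverse events from randomisation in controls but from first dose in the poractant arm, so timed poractant-arm events in between are missing from the by-arm AE tables

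*SAP*

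**What the plan says.** SAP 10.2 classifies each AE by its onset date and time.

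- **Poractant arm.** "Pre-treatment AE: if it starts before the first study medication administration"; "Treatment emergent AE (TEAE): if it starts on or after the first dose of study medication administration".
- **Control arm.** "Treatment emergent AE (TEAE): if it starts on or after the randomization date". The bracketed rule that follows makes clear that date and time of randomisation are meant.
- **Reporting.** "Pre-treatment AEs will be presented in the listings only". The listing is 16.2.7.1, titled "Pre-treatment Adverse Events (Intention-To-Treat Set)". In SAP 16.1 every AE table, 14.3.2.1 to 14.3.2.10, is restricted to treatment-emergent events or treatment-emergent adverse drug reactions.

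Protocol 7.1.2 limits the interval between the two starting points: in the poractant arm "the treatment must start soon after the randomization (max 2 hr)".

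Other parts of the plan use a common origin. SAP section 2 makes randomisation Day 1 for both groups, and SAP 7.9.3 counts study days from randomisation. Protocol 10.8 records AEs from screening, and Protocol 12.3.7 summarises AEs by group without limiting them to treatment-emergent events. SAP section 12, which lists departures from the protocol, mentions neither that limit nor the two origins.

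**The concern.** Counting from first dose gives comparable arms when both arms have a first dose. Controls here have none, so the SAP gives them an earlier origin and leaves the poractant arm with the later one. Follow-up ends at Day 28 after randomisation in both arms, so the poractant counting window is shorter by the length of the gap and nothing is added at the end to compensate.

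The trial is open label and allocation is known during the gap. An event then belongs to the randomised comparison whichever arm it occurs in, yet only the control event reaches a table. Exclusion depends on onset and not on outcome: a poractant-arm event that starts in the gap and later proves serious, severe or fatal is missing from those tables too. Its death would still count in mortality Table 14.2.4, so the efficacy and safety tables could disagree. Recruitment closed short of 70 (SAP section 12), so each patient weighs more in the percentages.

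**Working it through.** **The plan's own figures.** No figure in the documents measures this asymmetry. The one design calculation, 84% power for 42 against 28 patients, a 4-day difference and SD 5.5, reproduces (84.6% by normal approximation, 83.6% by noncentral t with 68 df). It does not enter this point.

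**Reading the rules side by side.** Take an AE that starts 60 minutes after allocation, and suppose the poractant patient is first dosed at 90 minutes (times chosen for illustration).

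- Control: onset at 60 min is later than randomisation at 0 min, so it is treatment emergent and tabulated.
- Poractant: onset at 60 min is earlier than first dose at 90 min, so it is pre-treatment and only listed.

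**Inputs for the size.** Maximum gap 2 h (Protocol 7.1.2); follow-up 28 days from randomisation (SAP section 2); planned arms of 42 and 28 (SAP section 5).

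- Follow-up per patient: 28 × 24 = 672 h.
- Share left out per poractant patient: 2/672 = 0.30%.
- Poractant time left out: 42 × 2 h = 84 patient-hours; 84/24 = 3.5 patient-days.
- Control time counted over the same 2 h: 28 × 2 h = 56 patient-hours; 56/24 = 2.3 patient-days.

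These are ceilings. They assume that every patient uses the full 2 h, that all 42 are enrolled, and that every onset is timed.

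**Event counts under assumed rates.** The documents give no AE rate. At an assumed constant 0.1 to 1 event per patient-day:

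- left out: 3.5 × 0.1 = 0.35 to 3.5 × 1 = 3.5 events;
- poractant-arm total over 28 days: 42 × 28 × 0.1 = 118 to 42 × 28 × 1 = 1,176 events.

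The share is 0.3% whatever constant rate is chosen. A higher rate in the first hours would raise it.

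**If the 2 h limit were exceeded.** SAP 10.2 sets no cap of its own. At assumed gaps of 6, 12 and 24 h the share is 6/672 = 0.9%, 12/672 = 1.8% and 24/672 = 3.6%.

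**The case against.** The strongest reply is that a first-dose origin is a conventional and defensible anchor, that the data are kept, and that about 0.3% of follow-up cannot change how the descriptive tables of an under-recruited proof-of-concept trial are read. SAP 7.5 and section 12 confirm that only descriptive summaries are planned. The points on size and consequence stand. The appeal to convention does not settle the matter, because the convention is applied to one arm only.

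Four stronger readings are tempting, and the documents do not support them.

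- **That every safety table is affected.** Only the AE tables use the treatment-emergent rule. The vital-sign and laboratory tables do not.
- **That the events are hidden.** They appear in Listing 16.2.7.1, and deaths are tabulated by arm in Table 14.2.4. Under SAP 7.4 an AE whose incomplete onset leaves its category open goes to treatment emergent first, so an untimed onset on the dosing day would be tabulated.
- **That harm from preparing the instillation is kept out of the tables.** Protocol 6.2.3 says "Before treatment, patients transiently will receive 100% oxygen", but describes catheter placement and lateral positioning as part of administration. The documents do not say whether the recorded administration time comes before or after those steps. Preparation for doses 2 and 3 falls after first dose and is counted in any case.
- **That a known number of events is lost.** Any count depends on an assumed rate, full use of the 2 h and planned enrolment.

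**Conclusion.** The asymmetry is real and follows directly from the wording of SAP 10.2. Poractant-arm AEs with a usable onset time between randomisation and first dose are left out of Tables 14.3.2.1 to 14.3.2.10, while control AEs in the same interval are counted. It is small: at most about 0.3% of follow-up, or 3.5 patient-days at planned enrolment, provided the 2 h limit is kept. For events in this gap the direction is fixed and can only favour poractant alfa. The case for acting rests on that direction, on the open-label design, on the absence of any declaration in SAP section 12 and on the low cost of correction. It does not rest on an expectation that the safety conclusions would change.

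**What to change.** 1. In SAP 10.2, define the between-arm AE tables by onset at or after the date and time of randomisation in both arms.
2. In Table 14.3.2.1, show poractant-arm events between randomisation and first dose as a separate line.
3. Keep the from-first-dose TEAE definition as a supplementary summary for the poractant arm only.
4. Record the change in SAP section 12.

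The cost is one sentence in SAP 10.2, one reference date in programming and one extra table line. There is one side effect: SAP 8.4 and 8.5 classify poractant-arm medications and procedures from first dose, so a drug started and stopped for a gap event could be labelled prior while the event itself is tabulated. A footnote should explain this. The change does not bring back patients randomised to poractant but never dosed, because the Safety Set in SAP 6.1 requires a dose. That is a separate matter.

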--	---

Clinical Study Code No.: CLI-050000-04	Version No.: 4.0
EUDRACT No.: 2020-002632-75 – IND No: 153286	Date: 02 MAR 2021

	
• Incidence of all the AEs, AEs related to poractant alfa (treated group) (ADRs), serious AEs (SAEs) and AEs leading to death will be summarized by group both in terms of frequency of patients with at least one AE and in terms of the frequency of AEs (number of events).• Vital sign values and their change from baseline will be summarized by group at each timepoint using descriptive statistics.• Laboratory parameters and their change from baseline will be summarized by group at each timepoint using descriptive statistics.
--	--

Clinical Study Code No.: CLI-050000-04	Version No.: 4.0
EUDRACT No.: 2020-002632-75 – IND No: 153286	Date: 02 MAR 2021

LIST OF ABBREVIATIONS AND DEFINITION OF TERMS

ADR	Adverse Drug Reaction
ARDS	Acute Respiratory Distress Syndrome
AE	Adverse Event
ABG	Arterial Blood Gas
ANOVA	Analysis of Variance
BAL	Bronchoalveolar Lavage
Cdyn	Dynamic compliance
CRA	Clinical Research Associate
CRF	Case Report Form
CRP	C-Reactive Protein
CRO	Contract Research Organization
Cstat	Static compliance
FPFV	First Patient First Visit
ET	Endotracheal
vvECMO	Veno Venous-Extracorporeal Membrane Oxygenation
ICH	International Conference on Harmonization
ICU	Intensive Care Unit
ITT	Intention to Treat
LPLV	Last Patient Last Visit
LBW	Lean Body Weight
MedDRA	Medical Dictionary for Regulatory Activities
MV	Mechanical Ventilation
NIV	Non-invasive Ventilation
PEEP	Positive End-Expiratory Pressure
PIP	Peak Inspiratory Pressure
Pplat	Plateau pressure
RR	Respiratory Rate
rtPCR	Real Time Polymerase Chain Reaction
SAE	Serious Adverse Event
SmPC	Summary of Product Characteristics
SOFA	Sequential Organ Failure Assessment
SUSAR	Suspected Unexpected Serious Adverse Reaction
TA	Tracheal Aspirate
TV	Tidal Volume

Clinical Study Code No.: CLI-050000-04	Version No.: 4.0
EUDRACT No.: 2020-002632-75 – IND No: 153286	Date: 02 MAR 2021

CONTENT

GENERAL INFORMATION	2
PROTOCOL OUTLINE	4
LIST OF ABBREVIATIONS AND DEFINITION OF TERMS	12
CONTENT	13
1. INTRODUCTION	15
1.1 BACKGROUND INFORMATION.....	15
1.2 STUDY RATIONALE.....	15
1.3 RISK/BENEFIT ASSESSMENT	17
2. STUDY OBJECTIVES	17
2.1 PRIMARY OBJECTIVE(S).....	17
2.2 SECONDARY OBJECTIVE(S).....	18
2.3 EXPLORATORY OBJECTIVE(S).....	18
3. STUDY DESIGN	18
3.1 STUDY DESIGN	18
3.2 END OF TRIAL DEFINITION.....	19
4. PATIENT SELECTION CRITERIA	19
4.1 PATIENT RECRUITMENT	19

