10. ADVERSE EVENT REPORTING

10.1 Definitions

An **Adverse Event** is “any untoward medical occurrence in a patient or clinical trial patient administered a medicinal product and which does not necessarily have a causal relationship with this treatment”.

An adverse event can therefore be any unfavourable and unintended sign (including abnormal laboratory finding), symptom, or disease temporally associated with the use of a medicinal product, whether or not considered related to the medicinal product.

An **Adverse Drug Reaction** is an “untoward and unintended responses to an investigational medicinal product related to any dose administered”.

All adverse events judged by either the reporting Investigator or the Sponsor as having a reasonable causal relationship to a medicinal product qualify as adverse reactions. The expression “reasonable causal relationship” means to convey in general that there are facts (evidence) or arguments meant to suggest a causal relationship.

The definition covers also medication errors and uses outside what is foreseen in the protocol, including misuse and abuse of the product.

A **Serious Adverse Event (SAE)/Serious Adverse Drug Reaction** is any untoward medical occurrence or effect that at any dose falls in one or more of the following categories:

- **Results in death**

Death is not an adverse event but an outcome. It is the cause of death that should be considered if it is regarded as the adverse event. The only exception to this rule is “sudden death” where no cause has been established; in this latter instance, “sudden death” should be regarded as the adverse event and “fatal” as its reason for being serious.

- **Is life-threatening**

Life-threatening refers to an event in which the patient was at risk of death at the time of the event. The term does not refer to an event which hypothetically might have caused death if it were more severe.

- **Requires hospitalisation or prolongation of existing hospitalisation**

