10.8 Recording Adverse Events

All Adverse Events occurring during the course of the study must be documented in the Adverse Event page of the electronic Case Report Form (eCRF). Moreover, if the Adverse Event is serious, the Serious Adverse Event Form must also be completed.

It is responsibility of the Investigator to collect all adverse events (both serious and non-serious) derived by spontaneous, unsolicited reports of patients, by observation and by routine open questionings.

For the purpose of this trial, “acute renal failure” occurrences will not be considered and recorded as adverse events, since well described as a part of the COVID19 syndrome, and highly prevalent in the involved population. They will be recorded as adverse events only if assessed as cause of patient’s death.

The recording period for Adverse Events is the period starting from the date of screening until the patient’s study participation ends.

Clinically significant abnormalities detected at study entry not due to a pre-existing condition or clinically significant changes at the following visits in the medical opinion of the investigator must be reported as adverse events in the eCRF.

If a clinically significant abnormal laboratory finding or other abnormal assessment meets the definition of an AE, then the AE eCRF page must be completed, as appropriate. A diagnosis, if known, or clinical signs and symptoms if diagnosis is unknown, rather than the clinically significant abnormal laboratory finding, should be reported on AE eCRF page. If no diagnosis is known and clinical signs and symptoms are not present, then the abnormal finding should be recorded.

For pharmacovigilance purposes, all SAEs should be followed-up in order to elucidate as completely and practically as possible their nature and/or causality until resolution of all queries, clinical recovery is complete, laboratory results have returned to normal, stable condition is reached or until the patient is lost to follow-up. Follow-up may therefore continue after the patient has left the study. In this case, the follow-up will continue with no timelines for related SAEs, while for unrelated SAEs the type and extent of follow-up undertaken will be determined for each individual case and will depend upon the nature (e.g. events with poor prognosis or which do not resolve), severity and medical significance of the event.

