12.3.7 Safety variables

Adverse Events

The number of patients who experienced at least one AE, AEs related to poractant alfa (treated group) (ADRs), serious AEs (SAEs) and AEs leading to death will be summarized by group. Summaries will be presented overall (number and percentage of patients having at least one event, total number of events) and by system organ class and preferred term (number and percentage of patients having at least one occurrence of that event).

Clinical Study Code No.: CLI-050000-04	Version No.: 4.0
EUDRACT No.: 2020-002632-75 – IND No: 153286	Date: 02 MAR 2021

All adverse events will be listed.

Vital Signs

Vital sign values and their change from baseline will be summarized by group at each timepoint using descriptive statistics.

Laboratory data

Laboratory parameters and their change from baseline will be summarized by group at each timepoint using descriptive statistics.

All laboratory data will be listed.

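### SAP 10.2 defines treatment-emergent by onset alone and tabulates nothing else, so an adverse event with screening onset that is later fatal, or worsens on the same record, is absent from the by-arm AE tables

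*SAP*

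**What the plan says.** SAP 10.2 splits adverse events into two classes by start time.

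- Poractant alfa: "Pre-treatment AE: if it starts before the first study medication administration", and "Treatment emergent AE (TEAE): if it starts on or after the first dose of study medication administration".
- Control: the same split at randomisation, "Treatment emergent AE (TEAE): if it starts on or after the randomization date".
- Reporting: "Pre-treatment AEs, and TEAEs will be presented separately. Pre-treatment AEs will be presented in the listings only".

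SAP 10.2 identifies an AE leading to death by its outcome field, but SAP 16.1 tabulates such events only when they are treatment-emergent (Table 14.3.2.10). The same restriction applies to every AE table from 14.3.2.1 to 14.3.2.10.

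The protocol is broader. Section 10.8 sets the collection period: "The recording period for Adverse Events is the period starting from the date of screening". The Safety Variables part of the protocol outline plans to summarise by group the "Incidence of all the AEs, AEs related to poractant alfa (treated group) (ADRs), serious AEs (SAEs) and AEs leading to death", and section 12.3.7 repeats that "serious AEs (SAEs) and AEs leading to death will be summarized by group". Neither place sets an onset limit. Section 10.1 explains how a death reaches the AE data: "Death is not an adverse event but an outcome". The event recorded is the cause of death, so the fatal outcome sits on a record that keeps its own onset date.

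**The concern.** Patients are already intubated and critically ill when AE recording starts, so an event can begin before the reference time and take its serious or fatal course after it. Whether a condition that is already present gets worse after endotracheal instillation is a tolerability question for this trial. The final SAP is descriptive throughout (SAP 7.5), so the by-arm AE tables are the safety comparison. A rule that looks only at onset can remove such cases from that comparison.

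The protocol supplies one concrete route. Under section 10.8, acute renal failure is recorded as an AE only when it is judged the cause of death. If such a record carries an onset date in screening, it is fatal by construction and still appears in no AE table.

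**Working it through.** No figure in the documents bears on this point; the 84% power calculation is not involved. The check is a reading of the rules, followed by simple arithmetic for scale.

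**1. The window.** SAP section 2 defines screening as intubation to randomisation. Protocol 7.1.2 requires randomisation within 48 hours of intubation, and the first dose within 2 hours of randomisation and within the same 48 hours. AEs with onset before the reference time can therefore exist, over at most 48 hours. The reference times also differ slightly: an event starting between randomisation and first dose is pre-treatment in the poractant alfa arm, while the same interval counts as treatment-emergent in controls.

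**2. The rule applied to one case.** Take a dosed patient with an AE that starts in screening and causes death on Day 10.

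| Output | Included? | Reason |
|---|---|---|
| Table 14.3.2.4 (serious) | No | Treatment-emergent events only |
| Table 14.3.2.10 (leading to death) | No | Treatment-emergent events only |
| Listing 16.2.7.1 (pre-treatment AEs) | Yes | Shows seriousness codes, including death |
| Table 14.2.4 (mortality, Day 21 and Day 28) | Yes | Deaths count whatever the AE onset |

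If the same event had started after the first dose, it would be in all the AE tables for which it qualifies.

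**3. Exceptions.** The only one is in SAP 7.4: an AE whose missing or incomplete date prevents allocation defaults to treatment-emergent. Nothing covers an AE with a known earlier onset that later worsens, becomes serious or is fatal.

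**4. Disclosure.** SAP 12 lists the dropped statistical analyses, the changed ITT definition and the missing cytospin and inflammatory-marker data. It does not list the restriction of the serious and fatal AE summaries to treatment-emergent events.

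**5. Scale.** One omitted patient changes an arm's percentage by 1/42 = 2.4 points (poractant alfa) or 1/28 = 3.6 points (control) at the planned size. The documents give no rate for such events. As an assumption only, let a proportion q of patients have one. The expected number in 70 is 70q, and the chance of at least one is 1 − (1 − q)^70:

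| Assumed q | Expected in 70 | Chance of at least one |
|---|---|---|
| 1% | 0.7 | 51% |
| 2% | 1.4 | 76% |
| 5% | 3.5 | 97% |
| 10% | 7.0 | 99.9% |

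SAP 12 says the study closed before reaching 70 and does not state the number enrolled. For any given q the expected count is therefore lower than shown, while each omitted patient weighs more if the arm is smaller.

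**The case against.** The strongest reply is that the loss is conditional. It arises for worsening only if the worsening stays on the original record. Protocol 10.8 requires clinically significant changes at later visits to be reported as AEs, section 10.1 treats complications arising in hospital as AEs, and SAP 10.2 foresees repeat records of one preferred term. A site could open a new record with a later onset, which would be treatment-emergent. This stands in part: neither document says that worsening of an open AE starts a new record, and the eCRF instructions are not available here. The count would then depend on site practice.

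The affected pool is also limited. SAP 8.3 classes conditions ongoing at screening as concomitant diseases, and the COVID-19 ARDS itself is medical history. A reader might infer that any post-dose deterioration of these is lost, but an AE first recorded when they worsen would have a post-dose onset. Air leak is a poor example, since pneumothorax is a named exclusion. These points stand.

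A reader might also infer a number of missing deaths by applying an assumed share of screening-onset events to the 30–70% ICU mortality in Protocol 1.1. The documents do not support this. They give no such share, the mortality range is background for COVID-19 ICU patients generally, and the planned arm sizes were not reached.

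Nor would a mismatch between Tables 14.3.2.10 and 14.2.4 prove the fault, because one uses the Safety Set and the other the ITT Set.

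Finally, the protocol leaves detail to the SAP and asks that all AEs be listed, which the SAP does. That makes the restriction arguable as elaboration. It does not explain why a by-group summary of fatal AEs should omit some of them without saying so.

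**Conclusion.** The point holds in conditional form. An AE recorded with onset between screening and the reference time that is later fatal, or that worsens on the same record, is absent from the by-arm AE tables. This follows from a stated rule and is narrower than Protocol 12.3.7, without disclosure in SAP 12. The fatal case is the firmest, because the outcome attaches to the causing event and its onset.

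The event does not vanish from the report: it remains listed, and a death by Day 21 or Day 28 remains in the mortality table. The loss is the by-arm serious or fatal AE count and its coding. Its size is 2.4 or 3.6 percentage points per omitted patient at the planned arm sizes. How many patients are affected cannot be derived from the documents. The conclusion assumes that at least some such events keep their original record and that their onset dates are complete enough to be classified.

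**What to change.** In SAP 10.2, count as treatment-emergent, in addition to events starting on or after the reference time:

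- any AE with a fatal outcome whose death falls on or after the reference time, whatever its onset. This is workable as it stands, since any death in a dosed patient or randomised control falls after that time;
- any earlier-onset AE whose recorded data show that it worsened in intensity or became serious on or after the reference time.

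Carry the flag through the affected tables (14.3.2.1 to 14.3.2.4, 14.3.2.8 and 14.3.2.10), with a footnote giving the number of events with pre-treatment onset in each arm.

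The documents show seriousness codes but no date on which an AE became serious. Where the eCRF holds no date for the change in intensity or seriousness, do not reclassify, because that could count events already serious before dosing as treatment-emergent. Show instead a separate row with the by-arm count of serious AEs with pre-treatment onset.

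Add the departure from Protocol 12.3.7 to SAP 12.

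The cost is SAP wording, a change to one derived flag, a footnote and possibly one table row; no new data are needed. The downside is that a few events with pre-treatment onset appear in the tables and need the footnote to be read correctly.
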